10 INTERIM AND IDMC ANALYSES

10.1 Interim Analysis

Interim analyses may be done at the discretion of the sponsor to allow for regulatory interactions and clinical development planning. Interim analyses will be performed and reviewed by an independent Vertex team not involved in the conduct of the study.

Interim analyses will be based on all data included in the IA data cuts.

10.1.1 General Consideration

General considerations, reporting conventions, and analysis methods specified for the final analysis apply to the IA, unless otherwise specified.

For the IA, the **TE period** will include the time period starting from the date of the first dose of study drug to either (1) the Safety Follow-up Visit, (2) ETT Visit if it replaces the Safety Follow-up Visit, (3) the date of the last dose + 28 days for subjects who do not have a Safety Follow-up Visit, or (4) the IA data cut date if subjects haven't completed the Treatment Period or haven't discontinued the study at the time of the IA data cut.

10.1.2 Background Characteristics

Refer to Section 9.2 for summary of background characteristics for IA. In addition, treatment ongoing will be summarized as disposition categories for IA.

10.1.3 Efficacy Analysis

Refer to Section 9.3 for efficacy analysis for IA.

10.1.4 Safety Analysis

Refer to Section 9.4 for safety analysis for IA.

10.1.5 Other Analysis

Refer to Section [9.59.4](#) for other analysis for IA.

10.2 Independent Data Monitoring Committee Analysis

Not applicable.

12 APPENDICES

Appendix A: Analysis Visit Windows for Efficacy, Safety, and Exploratory Assessments

Table 12-1 Analysis Visit Windows for Efficacy, Safety, and Exploratory Assessments			
Assessment	Visit¹	Target Study Day	Analysis Visit Window (in study days)^{2, 3, 4, 5}
Efficacy Assessments			

 • UPCR 	Baseline	Not applicable	<1
	Week 1	8	(1, 11]
	Day 15	15	(11, 18]
	Week 3	22	(18, 29]
	Week 5	36	(29, 50]
	Week 9	64	(50, 78]
	Week 13	92	(78, 106]
	Part B Week 4	120	(106, 134]
	Part B Week 8	148	(134, 162]
Part B Week 12	176	(162, 190]	

 • UACR 	Baseline	Not applicable	<1
	Week 1	8	(1, 11]
	Day 15	15	(11, 18]
	Week 3	22	(18, 29]
	Week 5	36	(29, 50]
	Week 9	64	(50, 78]
	Week 13	92	(78, 106]
Safety Assessments			

 • Serum Chemistry • Hematology • Coagulation 	Baseline	1	≤1 Pre-dose
	Week 1	8	[1 Post-dose, 11]
	Day 15	15	(11, 18]
	Week 3	22	(18, 29]
	Week 5	36	(29, 50]
	Week 9	64	(50, 78]
	Week 13	92	(78, 106]
	Safety Follow-up	Not applicable	Use nominal visit

 • Standard 12-lead ECG 	Baseline	1	≤1 Pre-dose
	Day 1 (2 hours post dose)	1	Nominal visit for all visits
	Week 1	8	
	Day 15 predose	15	
	Day 15 (2 hours post dose)	15	
	Week 3	22	
	Week 5	36	
	Week 9	64	
	Week 13	92	
	Safety Follow-up	Not applicable	

 • Vital Signs • Weight 	Baseline	1	≤1
	Week 1	8	[1 Post-dose, 11]
	Day 15	15	(11, 18]
	Week 3	22	(18, 29]
	Week 5	36	(29, 50]
	Week 9	64	(50, 78]
	Week 13	92	(78, 106]
	Safety Follow-up	Not applicable	Use nominal visit
Exploratory Assessments			

 • SF-36 	Baseline	1	≤1
	Week 5	36	[1 Post-dose, 64]
	Week 13	92	(64, 106]
	Safety Follow-up	Not applicable	Use nominal visit

Notes:

¹Visit name for analysis purpose is used to report data in tables and figures.

²The analysis visit windows will be applied using the following rules for both scheduled and unscheduled visits:

- a. If no numerical measurement is available within a visit window, the measurement will be considered missing for the visit.
- b. If there is more than 1 numerical measurement available within a visit window, use the following rules:
 - i. The measurement closest to the target day will be used; or
 - ii. If there are multiple measurements with the same distance from the target day, the latest measurement will be used. If the latest measurement cannot be determined, then unscheduled visit will be selected.
 - iii. If there are multiple measurements from the central laboratory and local laboratory with the same distance from the target day, the measurement from the central laboratory will be used.

³For measurements collected on the date of first dose of study drug in Treatment Period, if it cannot be determined whether the measurement is before or after the first dose:

- a. Scheduled measurement will be treated as pre-dose observation;
- b. Unscheduled measurement will be treated as post-dose observation.

⁴For safety assessment, the Safety Follow-up analysis visit will be based on nominal Safety Follow-up visit. If a subject doesn't have a nominal Safety Follow-up visit but has an ETT visit occurs 3 weeks (21 days) or later following the last dose of study drug, then the ETT visit will be mapped into Safety Follow-up analysis visit.

⁵UPCR and UACR at Week 5, Week 9 and Week 13 will be calculated by averaging maximum 3 nonmissing UPCR and UACR values measured within a 7-day period within the visit window.

- a. If there is only 1 assessment within the visit window, use the single value
- b. If there are more than 1 assessment within the visit window:
 - i. find the earliest assessment within the visit window, and then find the number of assessments within 7 days after the earliest assessment;
 - ii. find the second assessment within the visit window, and then find the number of assessments within 7 days after the second assessment;
 - iii. find the third assessment within the visit window, and then find the number of assessments within 7 days after the third assessment, if applicable;
 - iv. Compare the number of assessments from step i to iii, use the assessments from the step that has the maximum number. If number of assessments are the same from multiple steps, then use the step with the first assessment closest to target study day.

Derived Variable:

1. Missing first dose date or last dose date
 - If the first dose date is missing, use Day 1 visit date to impute.
 - If the last dose date is missing or partial date is reported, the last dose date will be imputed based on, in descending order priority, the Early Treatment Termination (ETT) visit date, last visit date before the Safety Follow-up, or the last study drug administration date from EC SDTM domain, as appropriate. The imputation algorithm will ensure the imputed last dose date does not exceed the study participation end date.
2. Electrocardiogram:

If ECGs are performed in triplicate at any visit and timepoint:

 - For summary purpose, the average of these ECGs at a specific visit and time point will be used as the ECG for that specific visit and time point.
 - For threshold analysis purpose, all reported ECG values will be used.
3. Systolic and diastolic blood pressures:

If systolic and diastolic blood pressures are performed in triplicate at any visit:

 - For summary purpose, the average of these systolic and diastolic blood pressures at a specific visit will be used as the systolic and diastolic blood pressures for that specific visit.
 - For threshold analysis purpose, all reported systolic and diastolic blood pressures will be used.

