11.3 Urine Sampling for UPCR, UACR, and Safety Laboratory Panel

Urine will be collected from the first morning void (predose) for use in efficacy and safety analyses. Efficacy analyses will include UPCR (primary endpoint) and UACR (exploratory endpoint), as calculated from protein, albumin, and creatinine measured in the urine. Safety assessments will include the urine laboratory parameters in Section 11.6.2. During the Screening, Week 5, Week 9, and Week 13 Visits, when 3 samples are collected on 3 separate days within a 7-day period, the third sample collected will be used for the safety laboratory and biomarker assessments; all 3 samples will be used for UPCR and UACR.

If the subject does not remember to collect their first morning void on the scheduled visit day, the subject may provide the sample on another day within the visit window.

Details about the collection and processing of urine samples will be provided in the Laboratory Manual.

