• *Hepatitis C Virus (HCV):* A blood sample will be collected for serology and nucleic acid testing. If the antibody test is positive, a nucleic acid test will be done.

Algorithm for assessing out of range laboratory values at Screening:

If one or more lab values NOT specified in the eligibility criteria (Section 8) are outside the normal range, the following choices are available:

- The subject may be excluded.
- The subject may be included if the lab value(s) are not clinically significant, as determined by the principal investigator (PI).
- The subject may be included if the lab abnormality is consistent with a pre-existing medical condition that is NOT excluded per protocol.
- Repeat the test for the individual lab assessment per the guidance in Section 9.1.1.1.

Pregnancy Testing for Female Subjects of Childbearing Potential (Section 11.6.5):

• Urine pregnancy tests will either be performed and analyzed at the site or, when there is a home health visit, at home using a home kit provided by the site/home health nurse. The urine pregnancy test on Day 1 must be negative before the first dose of study drug. Additional pregnancy tests may be required according to local regulations and/or requirements.

If a urine pregnancy test is positive, all study drug dosing will stop, and the pregnancy will be confirmed with a serum β -hCG test. If pregnancy is confirmed, the procedures outlined in Section 11.6.5.2 will be followed.

Additional Evaluations: Additional clinical laboratory evaluations will be performed at other times if judged to be clinically appropriate.

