7.2 Sample Size and Power

The sample size was not calculated based on power assumptions, because this is an estimation study. The primary endpoint is percent change from baseline in UPCR at Week 13. Assuming an SD of 0.672 (in log scale), a sample size of 10 subjects will provide a precision of 0.294 (in log scale) for the estimation of the Geometric Mean Percent Change (GMPC) from baseline in UPCR. The precision of the estimate corresponds to the half width of its 80% confidence interval (CI), in log scale.

Table 7-1 displays the expected size of the 80% CIs for the GMPC at various values of the observed GMPC. Approximately 10 subjects will be enrolled in each cohort.

Number of Subjects Completing	Assumption for SD in Log Scale	Observed Geometric Mean (corresponding percent reduction from baseline)			
		0.5 (-50%)	0.6 (-40%)	0.7 (-30%)	0.8 (-20%)
10	0.672	0.37, 0.67 (-63%, -33%)	0.45, 0.81 (-55%, -19%)	0.52, 0.94 (-48%, -6%)	0.60, 1.07 (-40%, 7%)

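### The SAP admits unscheduled urine results to the post-baseline UPCR and UACR visit values with no first-morning-void condition; the likely effect is small, but the rule is cheap to close.

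*SAP*

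**What the plan says.** Protocol Version 6.0, Section 11.3: "Urine will be collected from the first morning void (predose) for use in efficacy and safety analyses". Table 3-2 asks for three such voids on separate days within a week at Weeks 5, 9 and 13. It lets a subject who forgets the void on the visit day supply a predose sample on another day in the visit window.

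Protocol Section 11.6.2, under additional evaluations: "Additional clinical laboratory evaluations will be performed at other times if judged to be clinically appropriate". No void type is stated there. The urinalysis panel in Table 11-2 includes protein, creatinine and albumin, so an unscheduled panel can yield both ratios.

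SAP Section 9.1 places unscheduled data in the scheduled visit windows. Appendix A, note 2, repeats this for the table that covers UPCR and UACR: "analysis visit windows will be applied using the following rules for both scheduled and unscheduled visits". Within a window the value nearest the target day is used, and at equal distance the latest one. If that does not settle it: "If the latest measurement cannot be determined, then unscheduled visit will be selected".

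For Weeks 5, 9 and 13, note 5 averages at most three values within a 7-day period. It counts the assessments that follow the first, second and third assessment in the window, and then: "Compare the number of assessments from step i to iii, use the assessments from the step that has the maximum number". Ties go to the cluster whose first assessment is nearest the target day.

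The SAP does not mention the first morning void. Only the UPCR/UACR baseline is tied to named samples, the three screening voids used for eligibility.

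**The concern.** The protocol fixes the sample type for the endpoint; the SAP's selection rules ignore it. An unscheduled urine panel taken at any time of day competes on equal terms with the protocol void, and at single-value visits it can win outright. The primary endpoint is exposed through note 5.

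The study is very small. SAP Sections 9.3.1.3 and 9.3.1.4 plan no supportive or sensitivity analysis of the primary endpoint, and Section 9.1 plans no formal outlier handling. No planned analysis would therefore show the effect of a substituted value.

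**Working it through.** **Plan's own figure.** SAP Section 7.2 gives SD 0.672 (log scale), n = 10 and an 80% CI half-width of 0.294. Check: t(0.90, 9 df) × 0.672 / √10 = 1.383 × 0.672 / 3.162 = 0.294. It reproduces and is not in dispute.

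**Single-value visits (note 2).** Week 3 has target Day 22, and the protocol window is ±2 days. A scheduled void on Day 24 is 2 days from target; an unscheduled sample on Day 22 is 0 days away and becomes the Week 3 value. Part B visits may fall up to 2 weeks from target, so they are more exposed.

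**Week 13 (note 5).** The analysis window is Day 79 to Day 106 and the target is Day 92. Applying note 5 literally:

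| Scheduled days | Unscheduled days | Count from 1st, 2nd, 3rd assessment | Values used |
|---|---|---|---|
| 88, 90, 92 | 80 | 1, 3, 2 | the scheduled triplet |
| 88, 90, 92 | 87 | 4, 3, 2 | four values, cap of three, no rule for which |
| 88, 90, 92 | 79, 80, 81 | 3, 2, 2 (or 1) | the three unscheduled; triplet dropped |
| 91, 92 | 80, 82, 84 | 3, 2, 2 (or 1) | the three unscheduled; both scheduled dropped |
| 92 | 80, 83 | 2, 1, 1 | the two unscheduled; scheduled dropped |
| none | 79 | single value | the unscheduled value |

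The last column is the same whether 7 days means the start day plus 7 or seven calendar days counted inclusively. The bracketed counts are for the inclusive reading. In the third row only the first three assessments can start a cluster, so the triplet's own cluster is never considered.

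**Size.** The documents give no spot-to-first-morning ratio, so f = 1.3 to 1.5 in one subject is an assumption. With baseline unchanged, the geometric mean ratio is multiplied by r^(1/n). Here r = f if the spot void is the whole visit value, and r = (2 + f)/3 if it is one of three equal values. The primary analysis combines the cohorts (SAP Section 9.3.1.2), about 20 subjects at planned size.

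- Week 13, one of three values: r = 3.3/3 = 1.100 to 3.5/3 = 1.167. At n = 20: 1.100^(1/20) = 1.0048 and 1.167^(1/20) = 1.0077, a shift of 0.5% to 0.8%.
- Week 13, full substitution at n = 20: 1.3^(1/20) = 1.013 and 1.5^(1/20) = 1.020, a shift of 1.3% to 2.0%. An observed ratio of 0.50 would become at most 0.51.
- Single-void visit, one cohort of 10: 1.3^(1/10) = 1.027 and 1.5^(1/10) = 1.041, a shift of 2.7% to 4.1%.

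**Against precision.** If the SD of 0.672 also holds for the pooled set, the 80% half-width at n = 20 is 1.328 × 0.672 / √20 = 0.200. The Week 13 shifts on the log scale are 0.005 to 0.008 (one of three values) and 0.013 to 0.020 (full substitution). These are about 2% to 4% and 7% to 10% of that half-width.

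**The case against.** The strongest reply is that the void condition already exists: Protocol Section 11.3 is not limited to scheduled visits, and the SAP is based on the protocol. It stands to this extent: the SAP lacks a condition, but it does not direct anyone to use spot voids. It does not settle the matter, because Section 11.6.2 allows extra tests without naming a void type, and a programmer following Appendix A would apply no filter.

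It is also fair that the documents do not show that unscheduled urine panels will be common, or that they would be spot voids. The one stated provision for capturing local-laboratory results concerns blood safety samples. Windowing unscheduled data can also recover a visit value that would otherwise be missing, since the SAP does not impute.

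Three stronger readings are tempting and are not supported:

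- A reader might infer that a single unscheduled void readily pushes out the Week 13 triplet. Take Day 85 with voids on Days 88, 90 and 92. On the plus-7 reading there are four values, which still include the whole triplet. On the inclusive reading, Days 85, 88, 90 tie with Days 88, 90, 92, and the tie-break keeps the triplet.
- A reader might infer that clinically prompted samples bias UPCR upward. The documents give no data on direction.
- A reader might infer that the first morning void was chosen because UPCR varies within a person. Protocol Section 9.3.4.1 gives variability as the reason for three samples, and accuracy in standard practice as the reason for the void.

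**Conclusion.** The point holds as a defect in the SAP's selection rules. Unscheduled results compete equally for post-baseline UPCR and UACR values. They can replace the scheduled void at single-value visits, which serve exploratory endpoints. At Weeks 5, 9 and 13 they can create an undefined choice among four values or, in less common patterns, displace scheduled samples. The UPCR/UACR baseline is largely protected.

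The expected effect on the primary estimate is small relative to its planned precision. The sizes rest on an assumed 30% to 50% excess in one subject, and on about 20 pooled subjects; with fewer subjects the shift is larger. How often this would happen cannot be judged from the documents. A reader should not conclude that the primary result would be materially distorted. This is a cheap improvement worth making before the data are analysed.

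**What to change.** In SAP Appendix A, notes 2 and 5:

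- Limit UPCR and UACR analysis values to protocol-scheduled first-morning-void samples, plus first-morning-void make-ups for a missed scheduled sample.
- Put all other unscheduled UPCR and UACR values in a listing.
- Apply the 7-day rule after this filter.
- State which three values are averaged if more than three qualify.

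The cost is a few sentences and one programming filter; planned n and precision do not change. A few unscheduled values move to a listing, and an occasional visit value may be missing. Void type must be identifiable for make-up samples, and the documents do not show that it is recorded, so this should be checked first.

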The visit names for Part B were modified to reflect the time of the visit relative to the last dose of study drug.	Table 3-3
The Part B requirement to collect a confirmatory UPCR sample after the level returns to baseline was removed because Part B is optional and the requirement is an unnecessary burden for subjects.	Table 3-3
The blood pharmacokinetic (PK) sample was removed from the Safety Follow-up Visit (28 days after the last dose of study drug) because it is not needed for analysis.	Table 3-3
Clarified that the Postdose PK Sampling Visit is not required for subjects who complete an ETT Visit.	Table 3-3
The visit window for the Part A Week 13 Visit was changed from \pm 2 days to -2 days to ensure that the efficacy samples for the primary endpoint are collected while the subject is on treatment.	Table 3-2
Added 1 additional UPCR sample during Week 9 (for a total of 2 samples) to provide a more accurate measurement at this timepoint.	Table 3-2; Sections 11.3 and 11.6.2
Clarified the timing of visit windows.	Table 3-2 and Table 3-3
Clarified in several sections that Part B is optional.	Sections 2 and 9.1
Short form-36 (SF-36) was added at the Safety Follow-up Visit and as an exploratory endpoint for Part B to assess the sensitivity of this tool to changes in treatment (i.e., baseline, during treatment, and off treatment).	Table 3-3; Sections 2 and 7.2
Added a visit window for the Treatment Period Day 15 Visit of ±2 days to allow flexibility in visit scheduling.	Table 3-2

Change and Rationale	Affected Sections
Modified the requirement for the 3 urine samples collected during screening and Week 13 to be collected on separate days within a 7-day period, instead of requiring at least 1 day between 3 separate collections. This will allow additional operational flexibility without changing the intent of the assessment. The corresponding eligibility criteria were also updated.	Table 3-1 and Table 3-2; Sections 8.1, 9.3.4.1, 11.3, 11.6.2, and 12.3.3
Urine PK was removed from the secondary endpoints because urine PK will not be collected.	Sections 2 and 7
Added rationale for the study duration and dose based on clinical and nonclinical data.	Sections 5 and 9.3
Added an additional exclusion criterion: "Hypersensitivity to investigational medicinal product or to any of its excipients".	Section 8.2
Added exclusion of hemoglobin <10 g/dL to exclude subjects with clinically significant anemia.	Section 8.2

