p-nCG (urine)	X				X	X	X	X	(Sections 11.6.2 and 11.6.5). This can be collected in the same sample as the urine sample for efficacy, safety, and biomarker analysis.
VX-147 dosing				X		The last dose of Treatment Period 1 will be Day 14. The first dose of Treatment Period 2 will be on Day 15 after all predose assessments are completed. The last day of dosing will occur the day before the Week 13 visit. The first dose in each period must be administered under the supervision of site medical staff or a home health nurse. Subjects will be monitored for 4 hours after receiving the first dose of each Treatment Period. (Section 9.6).			

^c Day 1 urinalysis will be for safety and biomarker assessments. Efficacy assessments will not be done.

Protocol VX19-147-101, Version 6.0

Table 3-2 Study VX19-147-101: Part A Treatment Period 1, Treatment Period 2, and Early Termination of Treatment Visit

	Treatmen	nt Period 1		Trea	atment Perio	od 2			
	Day 1 Visit	Week 1 Visit	Day 15 Visit	Week 3 Visit	Week 5 Visit	Week 9 Visit	Week 13 Visit	Early	
Event/ Assessment ^a	Window: Day 1 (±0 days)	Window: Day 8 (±1 day)	Window: Day 15 (±2 days)	Window: Day 22 (±2 days)	Window: Day 36 (±2 days)	Window: Day 64 (±2 days)	Window: Day 92 (-2 days)	Termination of Treatment Visit ^b	Comments
Adverse events			Continu	ous from signi	ng of ICF th	rough SFUV			Section 11.6.1.
Medications review			Continu	ous from signi	ing of ICF th	rough SFUV			Section 9.4.

Table 3-3 Study VX19-147-101: Postdose PK Sampling, Safety Follow-up Visit, and Part B Off-treatment Follow-up Period

Event/Assessment	Postdose PK Sampling	SFUV 28 (± 7) Days	Part B: Optional Off-treatment Follow-up	Comments
	(Approximately 48 hours after the last dose of study drug) ^a	After Last Dose of Study Drug ^b	Visits ^c (Part B Week 4 ^b , 8, and 12)	
Subject visit	X	X	X (until UPCR returns to ≥90% of baseline level)	The visit may be performed by a home health visit or in the clinic at the discretion of the investigator (Section 9.3.5). For each visit, at least 1 interaction with the subject and investigator will occur by phone, video, or in the clinic (i.e., in person, phone, or telemedicine video conference) within 1 business day after the home health visit, which can be outside the visit window. See Section 9.1.3 for details about determining the last visit for Part B.
SF-36		X		To be completed before all other study assessments (Section 11.5.3).

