Standard 12-lead ECG		X		Complete after SF-36 and before other assessments after subject has been supine for at least 5 minutes. ECGs (Section 11.6.4), vital signs, and blood draws should be performed in said order.
Vital signs		X		Complete before other assessments listed below after subject has been at rest for at least 5 minutes; they should be seated during the assessment (Section 11.6.3). Blood pressure will be collected in triplicate.

^a The postdose PK sampling visit is required for all subjects, with the exception of those who complete an ETT Visit.

The SFUV and Part B Week 4 Off-treatment Follow-up Visit may occur on the same day, provided the visit windows are met for both visits.

Visit windows for Part B are as follows: Week 4 Visit (Day 120 ± 2 weeks), Week 8 Visit (Day 148 ± 2 weeks), Week 12 Visit (Day 176 ± 2 weeks).

Table 3-3 Study VX19-147-101: Postdose PK Sampling, Safety Follow-up Visit, and Part B Off-treatment Follow-up Period

On-treatment Follow-up reriou					
Event/Assessment	Postdose PK Sampling (Approximately 48 hours after the last dose of study drug) ^a	SFUV 28 (± 7) Days After Last Dose of Study Drug ^b	Part B: Optional Off-treatment Follow-up Visits (Part B Week 4 ^b , 8, and 12)	Comments	
Weight		X		Weight will be measured with shoes off and light weight closing (no outerwear). (Section 11.1).	
Abbreviated physical examination		X		In addition to the scheduled visits, symptom-directed physical examinations will occur at any time during the study if triggered by AEs or if deemed necessary by the investigator (Section 11.6.3).	
Serum chemistry		X Fasted		A blood sample will be collected following an overnight fast (Section 11.6.2).	
Hematology		X		A blood sample will be collected (Section 11.6.2)	
Coagulation		X		A blood sample will be collected (Section 11.6.2)	
VX-147 PK Sampling	X			A blood sample will be collected (Section 11.2.1).	
Urine sample		X	X	The first morning urine void will be collected and used for efficacy, safety, and biomarker analyses (Sections 11.3 and 11.6.2). Refer to sample handling guidelines to ensure samples are collected and submitted appropriately for analysis.	
β-hCG (urine)		X		All female subjects of childbearing potential (Section 11.6.2). This can be collected in the same sample as the other urine sample.	
Adverse events		gning of ICF through UV	NA	Section 11.6.1	

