9.3.4.1 UPCR

Percent change from baseline in UPCR at Week 13 was chosen as the primary endpoint because proteinuria is a characteristic feature of FSGS and 1 of its main prognostic factors. Urine samples will be collected for UPCR using the first morning void, which is standardly used in clinical practice to determine accurate urine protein levels. As UPCR is variable within an individual, 3 samples will be taken during screening, Week 5, Week 9, and Week 13; and the average of the 3 values will be used to determine baseline, Week 5, Week 9, and end-of-treatment UPCR values, respectively.

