9.2.5 Study Drug Exposure and Compliance

Study drug exposure (in days) will be calculated as (last date of dosing – first date of dosing) + 1, regardless of study drug interruption, and will be summarized descriptively based on the Safety Set by cohort and overall. Study drug exposure (in weeks) will be summarized in categories for Treatment Period: ≤ 1 week, >1 to ≤ 2 weeks, >2 to ≤ 3 weeks, >3 to ≤ 5 weeks, >5 to ≤ 9 weeks, >9 to ≤ 12 weeks, and >12 weeks using counts and percentages.

Study drug compliance will be calculated as $100 \times [1 - (\text{total number of days of study drug interruption}) / (\text{duration of study drug exposure in days})]$. A study drug interruption on a given day is defined as any interruption of the study drug on that day. A study drug interruption that continues through the end of the study participation (i.e., subject does not resume study drug before the end of the study participation) will not be included in the compliance calculation. Study drug compliance will be summarized descriptively based on the FAS by cohort and overall. It will also be summarized in categories: $<80\%$ and $\geq 80\%$, using counts and percentages.

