9.3.1.2 Analysis of the Primary Efficacy Variable

The primary efficacy endpoint will be analyzed based on combined Cohort 1 and Cohort 2. Subjects non-compliant with study drug will not be included in the analysis.

The primary analysis of the primary efficacy endpoint will be based on the following steps: (1) Log-transform the UPCR values to reduce skewness; (2) Calculate the mean of the change from baseline in log-transformed UPCR, corresponding standard error (SE) and 2-sided 80% CI; (3) The geometric mean and geometric standard error (GSE) will be calculated by back-transforming (exponential-transform) the corresponding estimates obtained in step (2). GMPC from baseline will be obtained as $[\text{geometric mean} - 1] * 100\%$. The corresponding 2-sided 80% CI will be calculated by $[\text{back-transforming (exponential-transform) the CI obtained in step (2)} - 1] * 100\%$.

The GMPC from baseline in UPCR at Week 13, GSE (%), along with the corresponding 2-sided 80% CI will be provided. In addition, the corresponding 2-sided 95% CI will be provided for descriptive purposes.

In addition, the primary efficacy endpoint will also be summarized in a similar way separately for Cohort 1 and Cohort 2.

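### The UPCR/UACR analysis windows ignore time since last dose, so for some early stoppers a single void taken 21 to 35 days off drug can become the Week 13 primary value

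*SAP*

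**What the plan says.** **Protocol (Version 6.0).** Table 3-2 sets the Week 13 visit at Day 92 (-2 days) and says of dosing: "The last day of dosing will occur the day before the Week 13 visit". Section 9.3.4.1 treats the Week 13 value as the end-of-treatment measure: "the average of the 3 values will be used to determine baseline, Week 5, Week 9, and end-of-treatment UPCR values". Section 12.3.3.1 averages up to 3 measurements taken during Week 13. The Version 2.0 summary of changes gives the reason for the one-sided window, which Version 6.0 keeps: to "ensure that the efficacy samples for the primary endpoint are collected while the subject is on treatment".

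Under Section 9.1.2.3, a subject who stops early attends an Early Termination of Treatment (ETT) Visit, then the SFUV at 28 (± 7) days after the last dose, and no further Part A visits. An ETT Visit 3 weeks or more after the last dose replaces the SFUV. Table 3-3 schedules urine at the SFUV and states its use: "The first morning urine void will be collected and used for efficacy, safety, and biomarker analyses".

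**SAP.** Table 12-1 gives UPCR and UACR a Week 13 window of (78, 106], applied to scheduled and unscheduled visits. Note 4, which is limited to safety assessments, says "the Safety Follow-up analysis visit will be based on nominal Safety Follow-up visit". Note 5 averages up to 3 values within 7 days and allows one: "If there is only 1 assessment within the visit window, use the single value". Section 9.3.1.2 says "Subjects non-compliant with study drug will not be included in the analysis" but does not define the term. Section 9.3.1.4 plans no sensitivity analysis.

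**The concern.** No rule in Table 12-1 or its notes asks whether the subject was still on drug when the urine was collected. The SAP sets Safety Follow-up data apart for laboratory tests, ECG, vital signs, weight and SF-36, but not for the primary variable.

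For an affected subject, the primary value is then one void taken three to five weeks after stopping, instead of an average of up to three at the end of treatment. Whether an early stopper contributes an on-drug value, an off-drug value or nothing depends on the dates of the last dose, the ETT Visit and the SFUV. That leaves the estimand unclear. The exploratory UPCR and UACR curves for the Treatment Period can also contain off-treatment data at Weeks 5, 9 and 13.

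**Working it through.** **1. Planned precision reproduced.** SAP 7.2 gives SD 0.672 (log scale), n = 10, two-sided 80% CI and half-width 0.294.
- Formula: t(0.90, n-1) × 0.672 / √n.
- n = 10: 0.294, which matches the SAP.
- n = 20 (both cohorts combined): 0.1995, about 0.200.

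**2. When the SFUV void reaches an analysis window.** Let L be the study day of the last dose. The SFUV falls on Days L+21 to L+35.
- It can fall in a window of Days a to b if L+35 ≥ a and L+21 ≤ b.
- It always does if L+21 ≥ a and L+35 ≤ b.

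| Window | Days | Can fall in window | Always falls in window |
|---|---|---|---|
| Week 5 | 30-50 | L = 1-29 | L = 9-15 |
| Week 9 | 51-78 | L = 16-57 | L = 30-43 |
| Week 13 | 79-106 | L = 44-85 | L = 58-71 |

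**3. When note 5 selects it for Week 13.** An ETT void may also lie in the window. ETT Visits were placed at L+1, L+3 and L+7. The ETT and SFUV voids are then at least 14 days apart and never share a 7-day set, so each counts as one assessment and note 5b(iv) takes the one nearer Day 92.

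| ETT Visit | SFUV void used on some permitted date | On every permitted date |
|---|---|---|
| L+1 | L = 44-80 | L = 58-71 |
| L+3 | L = 44-79 | L = 58-71 |
| L+7 | L = 44-77 | L = 58-71 |
| No ETT urine | L = 44-85 | L = 58-71 |

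For L = 58-71 with the ETT Visit by Day 78, the SFUV void is the only value in the window. Example: with last dose on Day 60 and ETT on Day 61 (Week 9 window), the SFUV is on Days 81 to 95 and its single void is the Week 13 value.

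**4. Completers.** The Week 13 visit is on Days 90 to 92, so the last dose is on Days 89 to 91. The SFUV is on Day 89+21 = 110 to Day 91+35 = 126, outside the window.

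**5. Does the non-compliance exclusion remove these subjects?** The only compliance formula is in SAP 9.2.5: 100 × [1 - interruption days / exposure days]. It leaves out "A study drug interruption that continues through the end of the study participation". The Day 60 stopper with no earlier interruption scores 100 × (1 - 0/60) = 100%.

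**6. Size of the effect.** The documents give no dropout rate and no off-drug course. Assume an on-drug ratio of 0.5 in the other subjects and an off-drug ratio r of 0.75 to 1.0 in one subject. The estimate is exp{[(n-1) ln 0.5 + ln r] / n} - 1.

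| n | r = 0.75 | r = 1.0 |
|---|---|---|
| 20 (combined, primary) | -49.0% | -48.2% |
| 10 (one cohort) | -47.9% | -46.4% |

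For n = 20 the log shift is ln(0.75/0.5)/20 = 0.020 to ln(1/0.5)/20 = 0.035. Divided by 0.1995, that is 10% to 17% of the half-width.

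**The case against.** The best counter-argument is that the effect is small and needs several conditions to coincide. A subject must stop in part of the treatment period and attend the SFUV. Even with full loss of effect, one subject moves the combined estimate by under 2 percentage points, toward no effect, in an estimation study without a power-based sample size. This stands, and it limits the severity.

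It can also be said that using the value nearest the scheduled time regardless of stopping is a recognised choice. Removing these values leaves the primary analysis closer to completers only, which looks more favourable if the effect fades off drug. That trade-off is real. But the SAP nowhere states such a strategy. It fits poorly with ending Part A visits at ETT, excluding non-compliant subjects, and restricting the value to samples taken during Week 13.

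The explicit on-treatment rationale appears only in an amendment summary. It is used here for purpose alone; the window it explains is still in force. If non-compliant was meant to cover early stopping, these subjects would drop out, but the SAP does not say so. The formula does still count interruptions that ended before the final stop, so the 100% score applies only to subjects with no earlier interruption.

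Finally, ETT and SFUV voids can be equally far from Day 92, and note 5 has no tie-break. If note 2b(ii) (latest measurement) applied, the upper limits of 80, 79 and 77 would become 81, 80 and 78. This changes nothing of substance.

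**Conclusion.** The concern holds and should be fixed. Followed exactly, the SAP can take its Week 13 primary value from one void collected 21 to 35 days after the last dose. It does so on every permitted SFUV date for a last dose on Day 58 to 71 (ETT done within 7 days of the last dose, or no ETT urine), and on some dates across as much as Day 44 to 85. An ETT Visit that replaces the SFUV can enter the same way, with no 35-day upper limit.

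The window ranges follow from the documents. The effect sizes rest on the assumed ratios and on one affected subject. No planned analysis would reveal the effect, although Protocol 12.3.3.1 promises sensitivity analyses for discontinuation.

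**What to change.** 1. Add a nominal Safety Follow-up row for UPCR and UACR in Table 12-1 and extend note 4 to them. SFUV voids, and ETT voids 21 or more days after the last dose, would then be ineligible for Weeks 1 to 13. Keep a void eligible for Part B Week 4 when the two visits share a day, and state what happens when they do not.
2. State a maximum lag after the last dose for Part A samples, for example 7 days. The Week 13 visit is last dose +1 and its voids span at most 7 days, so collection starting at the visit ends by last dose +7. Prompt ETT voids are also kept. A completer whose visit runs late could lose voids, so the limit should be chosen with that in mind.
3. Define non-compliant in SAP 9.3.1.2 and say whether it covers permanent early stopping.
4. Replace the statement in SAP 9.3.1.4 with a sensitivity analysis that includes post-discontinuation values under the present study-day rule. This shows how far the result depends on setting them aside.

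**Cost:** a few lines of SAP text and programming, and one extra table. Some early stoppers become missing at Week 13. Losing one takes the planned half-width from 0.200 (n = 20) to 0.205 (n = 19) combined, or from 0.294 (n = 10) to 0.313 (n = 9) in a cohort. With a 7-day limit, ETT voids 8 to 20 days after the last dose leave the primary analysis but stay in the sensitivity analysis.
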